4.1 Overall Design

This is a Phase 2A, placebo-controlled, randomized dose response study of the safety, PK, and efficacy of PCS12852 on gastric emptying rate assessed by the GEBT in patients with moderate to severe gastroparesis.

In this study, gastroparesis patients who have successfully completed Screening criteria (Visit 1) will return for a second Screening Visit (Visit 2) where the inclusion/exclusion criteria will be re-evaluated.

Visit 1 will include all safety labs and procedures (including an ECG) as well as the Columbia-Suicide Severity Rating Scales (C-SSRS) assessed by the investigator to confirm that the patient does not have any suicidal tendencies or ideation. If patients still meet study criteria when returning for Visit 2, a GEBT will be performed and the patient will be educated on completion of the ANMS GCSI-DD. Patients will complete the ANMS GCSI-DD for 7 days. The results from both the GEBT and the ANMS GCSI-DD during the Screening period will be considered the baseline values for these assessments.

The GEBT at Visit 2 and Visit 6 will be performed at the sites. Patients will be told to fast overnight (at least 8 hours) prior to coming to the site for the test. The patient will have their glucose tested both before and after the GEBT. The patient must have a fasting blood glucose of \leq 275 mg/dL to proceed with the GEBT. If the patient does not have a FBG \leq 275 mg/dL, they are permitted to come in the following day to perform the GEBT test. If the patient's FBG is not within range at Visit 6, the patient will be sent home with an additional dose of study medication and asked to return the next day to perform the GEBT.

Patients will return to the site for Day 1 (Visit 3 [Randomization]) where patients who meet the criteria for having moderate to severe symptoms based on the ANMS GCSI-DD will be randomized in a 1:1:1 ratio into three treatment groups, PCS12852 0.1 mg, PCS12852 0.5 mg or placebo. At Visit 3, patients will answer a series of questionnaires including the Patient Assessment of Gastrointestinal Disorders Symptom Severity Index (PAGI-SYM), Patient Assessment of Upper Gastrointestinal Disorders – Quality of Life (PAGI-QOL), Patient Global Impression of Severity (PGI-S) and the Patient Global Impression of Change (PGI-C). Patients will arrive in a fasted condition and have PK samples drawn prior to receiving the first dose and at the following times after the first dose, 0.5, 1, 2, 4, 6, and 8 hours. The ECG should be performed prior to the 4-hour PK draw between the 2- and 4-hour samples. The investigator will assess the patient through the C-SSRS as well as the CGI-S and CGI-I.

Patients will return to the site on Day 7 (Visit 4) and Day 14 (Visit 5) to undergo safety and tolerability assessments as per the Schedule of Assessments, along with the investigator assessing the patient for the C-SSRS to ensure the patient does not have any suicidal tendencies

Version 3.0 30 of 85 20 April 2022

or ideation. Sites will be asked to schedule the patient's visit so that the ECG can be performed approximately 4 hours after the patient's dose.

Patients will take their assigned treatment once daily for 28 days and will return to the site on Day 28 (Visit 6) for their final dose. On Visit 6, PK samples will be drawn and the GEBT will be repeated. During the treatment period, the patients will also complete the ANMS GCSI-DD. Each patient will be told to take one tablet from their assigned kit each day at approximately the same time each morning, at least 30 minutes prior to a meal (actual dosing times will be captured via a dosing diary), while fasting starting on Day 1 for 28 days.

On the morning of Day 28, after fasting overnight (for at least 8 hours), the patient will return to the site for Visit 6. At Visit 6, the patient will again compete the patient assessments and will have a PK sample drawn prior to receiving the final dose of PCS12852 or placebo and then have PK samples drawn at 0.5, 1, 2, 4, 6, and 8 hours post-dose. The ECG should be performed prior to the 4-hour PK draw between the 2- and 4-hour samples. The patient must have a fasting blood glucose (FBG) of ≤275 mg/dL to proceed with the GEBT. If the patient's FBG is not within range, the patient will be sent home with an additional dose of study drug and asked to return the next day to perform the GEBT and PK sampling. The GEBT test will be performed for 4 hours and will be administered approximately 30-60 minutes after the patient's final dose of study treatment. During the GEBT test, the site will prioritize taking the GEBT samples and then the PK samples. After the test is complete the patients will be discharged and then will return approximately 48-72 hours after Day 28 (Visit 6) to have a PK blood sample drawn. The patient will also return to the site 1 week after the Day 28 visit for a follow-up visit (Day 35/Visit 8).

The total study duration for each patient is expected to be approximately 8 weeks (3 weeks for Screening, 4 weeks for treatment, and 1 week for follow-up).

The SoA displaying assessments/tasks and time points is presented in Table 1.

4.2 Scientific Rationale for Study Design

This study has been designed to comply with recommendations in the FDA Guidance: Gastroparesis: Clinical Evaluation of Drugs for Treatment Guidance for Industry.

Several design features have been incorporated in the study in an effort to minimize bias, including double-blind design and random assignment of patients, helping to ensure that both known and unknown risk factors are distributed evenly among treatment groups. The use of a placebo control permits prospective comparison between the PCS12852 0.1 mg group and the PCS12852 0.5 mg group.

Version 3.0 31 of 85 20 April 2022

4.3 Justification for Dose

In the Phase 1 studies conducted with PCS12852, the product appeared to be safe and generally well-tolerated after both single (0.5 to 10 mg) and multiple doses (0.05 to 3 mg QD) (Section 2.1). The most frequently reported AE was headache. All AEs were generally mild and resolved without treatment. Therefore, the doses to be administered in the proposed Phase 2A study are 0.1 mg and 0.5 mg QD.

Data from the PCS12852-102 study showed a significant effect of PCS12852 at the 0.1 mg QD dose level on the gastric emptying rate assessed by the GEBT, but less effect was noted with the 0.05 mg daily dose. Safety for multiple dosing up to 3 mg daily has been well tolerated in the Phase 1 studies. In this Phase 2A study the effects of PCS12852 at the 0.1 and 0.5 mg dose levels vs. placebo will be evaluated on gastric emptying rate after 28 days of treatment.

4.4 End of Study Definition

The end of the study is defined as the date of the last visit of the last patient in the study.

A patient is considered to have completed the study if he/she has completed all 4 weeks of the study treatment and has had the last visit (Visit 8).

Independent of the end of study definition, all laboratory tests with values considered clinically significantly abnormal during participation in the study or within 30 days after the last dose of study treatment should be repeated until the values return to normal or baseline or are no longer considered clinically significant by the Investigator or medical safety physician.

The overall study will be stopped if ≥ 2 patients develop the same Grade 3 CTCAE (Common Terminology Criteria for Adverse Events) cardiac event or 1 patient develops a CTCAE \geq Grade 4 cardiac event.

Version 3.0 32 of 85 20 April 2022

5 Study Population

The study population will consist of male and female patients 18 to 80 years of age with moderate to severe IG or DG.

The patients must be able to provide written consent and meet all the inclusion criteria and none of the exclusion criteria based on Screening.

5.1 Inclusion Criteria

Patients are eligible to be included in the study only if all of the following criteria apply:

- 1. Has a documented diagnosis of moderate to severe DG or IG according to the ANMS GCSI-DD score during the Screening period (Score of >2 on average of the screening days).
- 2. Moderate to severe delay in gastric emptying rate as measured by the GEBT at Screening defined as GE half-time (t1/2) ≥ the 80th percentile of normative data as determined by Cairn Diagnostics.
- 3. Male or female patients 18 to 80 years of age, inclusive, at baseline.
- 4. Has continuous moderate to severe symptoms for gastroparesis (that is, chronic postprandial fullness, abdominal pain, postprandial nausea, vomiting, loss of appetite and/or early satiety) as assessed by the investigator for at least the past 3 months.
- 5. Has hemoglobin A1c (HbA1c) less than (<) 11 percent (%).
- 6. Has Body Mass Index range between 18 40.
- 7. Women of childbearing potential must have a negative serum pregnancy test at the Screening Visit and a negative urine pregnancy test at baseline before dosing.
- 8. Women of childbearing potential must use one of the following acceptable methods of contraception throughout the study (1 month prior to Screening through 1 month after last dose of study medication): oral contraceptive medication, intrauterine device (IUD), hormonal implants, injectable contraceptive medications, double-barrier methods, or tubal ligation.
- 9. Females who are postmenopausal (age-related amenorrhea ≥ 12 consecutive months and increased follicle-stimulating hormone [FSH] > 40 mIU/mL. If necessary, to confirm postmenopausal status, an FSH will be drawn at Screening) or who have undergone hysterectomy or bilateral oophorectomy are exempt from pregnancy testing.
- 10. Male patients must be willing to use acceptable contraceptive measures such as vasectomy or double barrier method and refrain from sexual activity with any

Version 3.0 33 of 85 20 April 2022

- female who is pregnant or lactating. Female partners of study participants are asked to use acceptable methods of contraception as listed in Inclusion #8 above.
- 11. Patient must be willing and able to swallow whole tablets.
- 12. Patient must be willing and able to comply with study procedures.
- 13. Compliance with the completion of the ANMS GCSI-DD, defined as approximately 80% diary completions, during the screening period. For those patients whose compliance is measured to be <80%, the final decision to randomize a patient will be made by the Investigator and the Sponsor (or designee).
- 14. Patient must be willing and able to provide signed, informed consent.

5.2 Exclusion Criteria

Patients are excluded from the study if any of the following criteria apply:

- 1. Has acute, severe gastroenteritis and pronounced dehydration in the past 48 hours prior to Screening, chronic parenteral feeding or persistent severe vomiting.
- 2. Has known hypersensitivity to Spirulina, egg, milk products or wheat allergens.
- 3. Has a known disturbance of small intestinal absorption, exocrine pancreatic function, liver metabolism or pulmonary function.
- 4. Has a history of anorexia nervosa or bulimia.
- 5. Previous history of bezoars (the presence of retained liquid, bile, or small amounts of poorly organized food residue is permitted).
- 6. Prior surgery involving any gastrointestinal surgery, including the luminal gastrointestinal (GI) tract (cholecystectomy and appendectomy are permitted if performed greater than (>) 3 months prior to baseline GEBT).
- 7. Any abdominal or pelvic surgery within the past 3 months.
- 8. Known or history of the following GI conditions: inflammatory bowel disease; irritable bowel syndrome with diarrhea; or any other active disorder that could explain symptoms in the opinion of the investigator.
- 9. Has active diverticulitis, diverticular stricture, and other intestinal strictures.
- 10. Has feeding or decompression tubes and/or a gastric pacemaker.
- 11. Has had Botox pyloric injections within the prior 3 months.
- 12. Has had diabetic ketoacidosis (within the prior 4 weeks).
- 13. Currently taking Glucagon-like peptide-1 (GLP-1) agonists, e.g. exenatide, liraglutide, semaglutide or dulaglutide, or pramlintide.
- 14. Has severe psychiatric illness (including suicidal tendencies or ideation) or neurological illness.
- 15. History or suspicion of alcohol, barbiturate, amphetamine or narcotic abuse.

Version 3.0 34 of 85 20 April 2022

- 16. Use of narcotics/opioids, drugs used to treat gastroparesis within 3 days of the Screening GEBT test.
- 17. Anticipated concurrent use of a strong Cytochrome P450 (CYP) inhibiting or inducing drug (listed in Section 6.7.1) that would significantly alter the metabolism of PCS12852 and/or its metabolites during the course of the study (after Screening)
- 18. Fever (> 38°C), or chronic, persistent, or recurring infection(s) at Screening or baseline.
- 19. Clinically significant cardiac disease including but not limited to unstable angina, acute myocardial infarction within 6 months of baseline, and arrhythmia requiring therapy.
- 20. Patient has QTcF interval ≥ 480 milliseconds on Screening ECG; a second Screening ECG may be done at the Investigator's discretion but the average of the two QTcF screening intervals must not be ≥ 480 milliseconds.
- 21. History of cerebral hemorrhage, cerebrovascular accident, transient ischemic attack, gastrointestinal bleeding, or retinal hemorrhage within 6 months of baseline.
- 22. Patient has active or history of neoplastic disease (except for adequately treated non-invasive basal cell and/or squamous cell carcinoma of the skin or carcinoma in situ of the cervix) within the past 5 years prior to baseline.
- 23. Presence of clinically significant medical condition(s) including but not limited to: renal, hepatic, cardiovascular, hematological, gastrointestinal, endocrine, pulmonary, neurological, psychiatric, substance abuse, and/or any other clinically significant disease or disorder, which in the opinion of the Investigator (by its nature or by being inadequately controlled), may put the patient at risk due to participation in the study, influence the results of the study, and/or affect the patient's ability to complete the study.
- 24. History of or current diagnosis of active tuberculosis (TB); undergoing treatment for latent TB infection (LTBI); untreated LTBI (as determined by documented results within 3 months of the Screening Visit of a positive TB skin test with purified protein derivative with induration > = 5 mm, a positive QuantiFERON-TB test or positive or borderline T-SPOT [Elispot] test); or positive TB test at Screening. Patients with documented completion of appropriate LTBI treatment would not be excluded and are not required to be tested.
- 25. Vaccination with live or live-attenuated virus vaccine within 1 month prior to baseline. Vaccines for COVID-19 are allowed.

Version 3.0 35 of 85 20 April 2022

- 26. The results of the following laboratory tests performed at the central laboratory at Screening meet any of the criteria below:
 - a. Hemoglobin $\leq 8.0 \text{ g/dL}$ (International System of Units: $\leq 80 \text{ g/L}$)
 - b. White blood cells $< 3.0 \times 10^3 \text{ cells/mm}^3 \text{ (SI: } < 3.0 \times 10^9 \text{ cells/L})$
 - c. Neutrophils $< 1.0 \times 10^3$ cells/mm³ (SI: $< 1.0 \times 10^9$ cells/L)
 - d. Lymphocytes $< 0.5 \times 10^3 \text{ cells/mm}^3 \text{ (SI: } < 0.5 \times 10^9 \text{ cells/L})$
 - e. Platelets $< 100 \text{ x } 10^3 \text{ cells/mm}^3 \text{ (SI: } < 100 \text{ x } 10^9 \text{ cells/L})$
 - f. Alanine aminotransferase (ALT), aspartate aminotransferase (AST), and/or alkaline phosphatase (ALP) ≥ 2 x upper limit of normal (ULN)
 - g. Total bilirubin level ≥ 2 x ULN unless the individual has been diagnosed with Gilbert's disease and this is clearly documented
 - h. Estimated glomerular filtration rate < 40 mL/min/1.73 m^2 based on the Modification of Diet in Renal Disease formula
 - i. Creatinine $\geq 3 \text{ mg/dL}$
 - j. Positive human immunodeficiency virus serology
 - k. Evidence of active Hepatitis B Virus infection
 - 1. Evidence of active Hepatitis C Virus infection
- 27. Women who are pregnant or breastfeeding.
- 28. Any other medical condition, serious intercurrent illness, or extenuating circumstance that, in the opinion of the Investigator, would preclude participation in the study.
- 29. Use of any investigational product within 30 days prior to baseline or currently enrolled in another study that involves clinical interventions.
- 30. Currently taking known P-gp and BCRP inhibitors or inducers and gastric acid reducing agents. E.g., proton pump inhibitors or H2 receptor antagonists

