5.3 Lifestyle Considerations

Abuse of alcohol, barbiturates, amphetamines or narcotics is restricted as indicated in Section 5.2. Smoking is prohibited at least 24 hours prior to the Screening GEBT and during the conduct of the study. There are no other specific lifestyle restrictions in the study.

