5.4 Screen Failures

Screen failures are defined as patients who consent to participate in the clinical study but are not subsequently enrolled in the study.

Version 3.0 36 of 85 20 April 2022

Individuals who do not meet certain criteria (e.g. lab values) for participation in this study (screen failure) may be rescreened. The GEBT test will not be repeated on a patient that does not meet GEBT entry criteria.

6 Study Treatment and Concomitant Therapy

Study treatment is defined as any investigational treatments, marketed product, or placebo, or intended to be administered to a study patient according to the study protocol.

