6.3 Measures to Minimize Bias: Randomization and Blinding

Patients who have successfully completed Screening criteria (Visit 1 and Visit 2) will return for a Randomization visit (Visit 3) where the inclusion/exclusion criteria will be evaluated and patients who meet the criteria will be randomized in a 1:1:1 ratio into one of the three treatment groups, PCS12852 0.1mg, PCS12852 0.5mg or placebo via Interactive Response Technology (IRT). The planned sample size to be randomized is 24 patients. The randomization to treatment groups will be stratified by type (IG, DG), enrolling at least 2 patients of each type in each treatment group.

The list of treatment allocations will be kept in a secure location by the CRO until approval to unblind is provided for the final analysis. Access to the treatment allocations will be monitored by Regulatory Affairs/Quality Assurance; any access to the allocations prior to unblinding the study will be documented by Regulatory Affairs/Quality Assurance and included in the Clinical Study Report.

Table 4 Measures to Minimize Bias

Study using IRT	All patients will be centrally randomized using an Interactive Response Technology (IRT). Each patient will be assigned a unique number (randomization number) that encodes the patient's assignment to one of the 3 arms of the study, according to the randomization schedule using a validated computer program. Details of the procedure are described in the IRT Manual provided to all sites.
	Study treatment will be administered/dispensed at the study visits as summarized in the SoA (Table 1).
	Returned study treatment should not be re-dispensed to the patients.

Version 3.0 38 of 85 20 April 2022

Blind break (IRT)

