6.7.1 Prohibited Treatments

The class of drugs prohibited in the study are those that affect GI motility, either positively or negatively, and therefore could confound the assessment of the efficacy of the study treatment on the signs and symptoms of gastroparesis.

Prohibited concomitant treatment includes cannabis, opioids, GLP-1 agonists (e.g. exenatide, liraglutide, semaglutide or dulaglutide, or pramlintide), cisapride, tegaserod, prucalopride, metoclopramide, bethanechol, domperidone and erythromycin or any other medications that are contraindicated for patients with gastroparesis.

Version 3.0 40 of 85 20 April 2022

IMPORTANT: Patients should be instructed to consult with the Investigator before taking any new medication or changing medications and/or dosing regimens throughout the study.

Drugs that are known to be strong inhibitors or inducers of Cytochrome P450 (CYP) (most likely CYP3A4 and CYP1A2) may significantly alter exposure to the investigational product, and as such, are strictly prohibited while on the study. Examples of CYP inhibitors include cimetidine, ciprofloxacin, fluvoxamine, clarithromycin, diltiazem, grapefruit juice, and itraconazole. Examples of CYP inducers include carbamazepine, phenobarbital, tobacco, and St. John's wort.

P-glycoprotein (P-gp), breast cancer resistance protein (BCRP), and gastric acid reducing agents may also significantly alter the exposure of the investigational product and as such, are strictly prohibited while on study. Examples of P-gp inhibitors include cyclosporine, amiodarone, and itraconazole as well as BCRP inhibitors include novobiocin, sulfasalazine and cyclosporine A which may potentially increase the systemic exposure. Examples of P-gp inducers include carbamazepine, phenytoin and rifampin. Examples of BCRP inducers and gastric acid reducing agents include venlafaxine, apalutamide and dovitinib as well as PPIs (esomeprazole, lansoprazole, omeprazole, etc), H2 blockers (ranitidine, famotidine, nizatidine) which may potentially decrease the systemic exposure.

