6.7.2 Permitted Treatments

Any medication or vaccine (including over-the-counter or prescription medicines, vitamins, and/or herbal supplements) that the patient is receiving at the time of enrollment or receives during the study must be recorded in the eCRF along with:

- indication
- dates of administration including start and end dates
- dosage information including dose and frequency

Diabetic gastroparesis patients enrolled in the study will likely consist mostly of patients receiving one or more prescription medications for blood-glucose control. Good clinical practice allows for frequent adjustment of medication by patients and their health care providers to minimize large fluctuations in glycemia, and this practice is encouraged in this study.

It should be remembered that certain diabetic drugs (see Section 6.7.1) delay gastric emptying and are prohibited during this study. Other therapy considered necessary for the patient's welfare

Version 3.0 41 of 85 20 April 2022

may be given at the discretion of the Investigator. If the permissibility of a specific medication/treatment is in question, please contact the Medical Monitor.

The Medical Monitor or designee should be contacted if there are any questions regarding concomitant or prior therapy.

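### No drug-free interval before the baseline breath test is set for cannabis, GLP-1 agonists or pramlintide, although Section 6.7.1 bars all three as motility confounders

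*Combined protocol and SAP*

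**What the plan says.** **On-study ban.** Section 6.7.1 prohibits drugs that change gut motility in either direction, because they could confound the efficacy assessment: "Prohibited concomitant treatment includes cannabis, opioids, GLP-1 agonists", with pramlintide in the same bracket. Section 6.7.2 adds that certain diabetic drugs "delay gastric emptying and are prohibited during this study".

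**Eligibility (Section 5.2, repeated in the Synopsis).** Exclusion 16 removes patients with use of narcotics/opioids or "drugs used to treat gastroparesis within 3 days of the Screening GEBT test". Exclusion 13 removes patients "Currently taking Glucagon-like peptide-1 (GLP-1) agonists"; pramlintide closes the same sentence under the same condition. Cannabis appears in no criterion. Table 6 (Appendix 2) puts THC in the screening urine drug screen, but no section says what a positive result leads to.

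**Other controls.** Section 5.3 states: "Smoking is prohibited at least 24 hours prior to the Screening GEBT and during the conduct of the study". Section 6.7.3 advises strongly against drugs that may affect the efficacy evaluations from Visit 1 on. Patients passing Visit 1 "will return for a second Screening Visit (Visit 2) where the inclusion/exclusion criteria will be re-evaluated" (Section 4.1). Section 6.7 requires a record of drugs in use at enrollment or taken later.

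**Role of the test.** The Visit 2 GEBT decides entry (inclusion 2), is the baseline for the primary endpoint (Section 4.1) and is the ANCOVA covariate (Section 9.2.2). Section 5.4 adds: "The GEBT test will not be repeated on a patient that does not meet GEBT entry criteria".

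**The concern.** Opioids are both prohibited on study and given an interval before the baseline GEBT, so the plan did not rely on the on-study ban alone to protect that test. Cannabis, GLP-1 agonists and pramlintide are prohibited for the same stated reason, yet none has an interval, and no reason is given for the difference.

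A patient whose last dose was shortly before Visit 1 can therefore be tested, enter the trial and carry a baseline measured soon after an exposure that the plan calls confounding. If the drug had slowed emptying, the patient may qualify without the intended underlying delay, and the arm's mean change from baseline is inflated. If it had sped emptying, an eligible patient may fail a test that cannot be repeated. Because a drug stopped before enrollment need not be recorded, the affected patients might not be identifiable afterwards.

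**Working it through.** **1. The rules side by side**

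| Drug | Barred on study (6.7.1) | Eligibility rule (5.2) | Interval before Screening GEBT |
|---|---|---|---|
| Opioids | yes | exclusion 16 | 3 days |
| Gastroparesis drugs | yes (several named) | exclusion 16 | 3 days |
| GLP-1 agonists | yes | exclusion 13, current use | none |
| Pramlintide | yes | exclusion 13, current use | none |
| Cannabis | yes | none | none (smoking: 24 hours, Section 5.3) |

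Visits 1 and 2 share one window, Day -21 to Day -1, with no minimum gap (Table 1).

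**2. The plan's own power figure**

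Inputs (Section 9.3): 8 per arm, SD 15, difference 25, two-sided alpha 0.025, stated power 80%. Noncentrality = 25 / (15 × √(2/8)) = 25 / 7.5 = 3.33. The two-sample t-test (14 df) gives 78.4%. Pooled three-arm error gives 81.0% (20 df) or 81.3% (21 df). The stated 80% is reproduced. For the analysis in Section 9.2.2 (three arms plus one covariate, 24 − 4 = 20 df) with a Dunnett critical value of 2.38, power is 82.1%. That is the reference below.

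**3. Effect of a shifted baseline**

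The documents give no frequency, size or persistence of drug effect. Assumed: k = 1 or 2 affected patients of 24; baseline AUC shifted by d = 10 to 25 units; Day 28 unaffected; baseline-to-Day-28 correlation r = 0.3 to 0.7; residual SD 15 when nobody is affected.

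- p = k/24; added baseline variance v = p(1 − p)d²
- true baseline variance s² = 225/(1 − r²); reliability L = s²/(s² + v)
- residual variance = s²(1 − r²L)
- shift of one arm's adjusted mean from one affected patient = d·r·L/8
- shift in mean raw change = p·d

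Worst corner (k = 2, d = 25, r = 0.7): v = (2/24)(22/24)(625) = 47.74; s² = 225/0.51 = 441.18; L = 441.18/488.92 = 0.902; residual variance = 441.18 × (1 − 0.49 × 0.902) = 246.1, so SD 15.69; adjusted shift = 25 × 0.7 × 0.902/8 = 1.97; raw change shift = 50/24 = 2.08.

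| k | d | Residual SD (r = 0.3 to 0.7) | Power | Adjusted shift | Raw change shift |
|---|---|---|---|---|---|
| 1 | 10 | 15.01–15.06 | 82.1–81.8% | 0.37–0.87 | 0.42 |
| 1 | 25 | 15.07–15.38 | 81.8–80.1% | 0.85–2.07 | 1.04 |
| 2 | 10 | 15.02–15.12 | 82.0–81.5% | 0.36–0.86 | 0.83 |
| 2 | 25 | 15.12–15.69 | 81.5–78.4% | 0.79–1.97 | 2.08 |

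**4. Sensitivity**

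- If 15 is the SD of the change, then s² = 225/(2(1 − r)). Unaffected power is 95.2%, 92.0% and 88.2% for r = 0.3, 0.5 and 0.7. With k = 2 and d = 25 it is 94.8%, 90.4% and 84.5%, a loss of at most 3.7 points.
- Simulated ANCOVA (20,000 trials) gives 80.5% unaffected and 75.9% in the worst corner, a loss of 4.6 points. Reversing the direction of the shift gives the same 75.9%.
- The simulated mean contrast stays at 24.9–25.1 throughout, against a true 25.
- Over the plan's own SD range of 10 to 35, power runs from 99% to 19%.

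**The case against.** Much of the gap for GLP-1 agonists and pramlintide is already closed. A current user fails exclusion 13 at Visit 1, eligibility is rechecked at Visits 2 and 3, and waiting for central-laboratory results makes a same-day move to Visit 2 unlikely. Section 6.7.3 reaches the period between the visits, and the Section 6.7.1 ban arguably does too. This largely stands. It leaves a last dose just before Visit 1, which neither section addresses. Laboratory turnaround is not a rule, and Section 6.7.3 discourages rather than forbids.

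Cannabis is partly covered. Use for symptom relief could be read as a gastroparesis drug under exclusion 16, smoking has its 24-hour rule, and exclusions 23 and 28 leave room for investigator judgment. But these controls depend on interpretation or discretion, and the smoking rule does not reach other forms.

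A reader might infer more than the documents support:

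- *That the treatment comparison is biased.* The baseline GEBT precedes randomization, so any exposure affects all arms alike in expectation. Only chance imbalance remains.
- *That pramlintide was overlooked.* It has the same current-use bar as GLP-1 agonists.
- *That a particular washout for long-acting GLP-1 agonists follows.* The documents say nothing about how long any of these effects last, nor in which direction cannabis acts. They mention delay only for certain diabetic drugs.

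**Conclusion.** The point holds as a minor one. The plan treats these three as motility confounders but sets no interval for them before the test on which entry and the primary baseline rest. The gap is clearest for cannabis, which no criterion names.

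Under the assumptions above, the loss is about 4 power points at most by formula (4.6 in simulation), and only if 2 of 24 patients are each shifted by an amount equal to the whole target difference. One affected patient moves an arm's adjusted mean by 0.4 to 2.1 units, roughly 1.5 to 8% of the 25-unit target. This is small beside the uncertainty in the SD. The gain from a change is a cleaner entry test and baseline, not the removal of a between-arm bias. The count, the shift and the persistence of effect after stopping are all assumed.

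**What to change.** - **Exclusion 16 (Section 5.2 and Synopsis):** extend the existing 3-day period before the Screening GEBT to every motility-affecting drug in Section 6.7.1, naming cannabis in any form, GLP-1 agonists and pramlintide. Leave any longer period for long-acting agents to the sponsor's clinical team. Keep exclusion 13 for current users.
- **Before the Visit 2 GEBT:** check history and the THC result. Postpone the test within the screening window if there was use in the period, or if the investigator judges that a positive THC screen reflects such use. The check must come first, because a failed GEBT cannot be repeated.
- **Recording:** capture last-use dates for these drugs even when they were stopped before enrollment.

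The cost is eligibility wording in two places and one eCRF field. A 3-day postponement fits: with seven diary days needed before Day 1, Visit 2 can fall about 13 to 14 days after a Visit 1 on Day -21. A longer interval set by the clinical team would have to be checked against that room. The downside is slightly slower screening, mainly of diabetic patients. The plan requires "enrolling at least 2 patients of each type in each treatment group", so at least 2 × 3 = 6 diabetic patients are needed.
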